- Goal: Evaluate change in time since treatment; administer perturbation tasks (NYU/MSU only) and accompanying perception tasks (all sites).
- See 1-Checklist for CRESULTS_Evaluation_PostTx2_RCT_ALLTasks (NYU/MSU) or 1-Checklist for CRESULTS_Evaluation_PostTx2_RCT_NoPerturbation (Syracuse) in CRESULTS Planning Folder/4c - Evaluation_COVID_CRESULTS/Post-Tx Evaluation 2 - RCT
- Probes for /r/ (if a child is being evaluated more than 6 weeks post treatment, don't administer probes; use 1-Checklist for CRESULTS_Evaluation_PostTx2_RCT_NoProbes)
- Head-had identification task
- Head-had discrimination task
- Reflexive perturbation task (NYU/MSU only)
- Adaptive perturbation task (NYU/MSU only)

12. Analysis Plan

- All analyses will be conducted following the intent-to-treat principle. For participants who drop out, missing data will be multiply imputed based on information collected about them prior to their loss to follow-up.
- For our primary outcome (Acquisition), we will fit a multilevel model with measures nested within study participants and words. The dependent variable will be F3-F2 distance in /r/ targets produced in each day of Phase 1 treatment. The primary independent variable of interest is group (traditional motor-based treatment versus biofeedback, with visual-acoustic and ultrasound biofeedback types pooled for this analysis). The model will also adjust for site, performance response category based on Dynamic Assessment (high responder versus low responder), acquisition day (1, 2, or 3, treated as categorical), and pre-treatment accuracy (mean F3-F2 distance across /r/ sounds in the word probe elicited in the first pre-treatment evaluation). If a within-session time trend is supported by the data, we will extend the model to account for time trends across trials within each day of treatment. Random intercepts will be included to reflect the fact

MASTER PROTOCOL FOR C-RESULTS RCT

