that observations are nested within speakers and words, and random slopes that improve overall model fit (for speaker, acquisition day; for word, performance response category and pre-treatment accuracy) will be retained following model comparison using likelihood ratio tests. Likelihood ratio tests will also be used to assess the significance of fixed effects and interactions in the final model. Likelihood ratio tests will also be used to test the hypothesis of an advantage for biofeedback over MBT. Tests will be performed in two different model specifications. In one, the overall effect across days will be tested by focusing on the coefficient on the treatment variable. The other specification will interact the treatment variable with time in order to test whether the effect varies across days, since the hypothesized advantage for biofeedback over MBT could emerge as early as the first day or as late as the third day of Phase 1 (Acquisition). Although a positive effect of biofeedback is hypothesized, two-sided hypothesis tests will be used to be conservative.

- For our secondary outcome (Generalization), we will use a linear mixed-effects model to examine word probe data collected in one immediate pre-treatment and one immediate post-treatment session. The outcome variable, “ \hat{p} -correct,” will reflect the proportion of naïve listeners who rated the /j/ sound in a given production as correct. Independent variables will include time point (pre- versus post-treatment) and treatment group (biofeedback versus MBT), as well as the interaction between them. As for our primary measure, the model will adjust for site, performance response category based on Dynamic Assessment, and pre-treatment accuracy. Random intercepts for speaker, item, and listener will be included. Random slopes of response category and pre-treatment accuracy on word will be included only as warranted by model comparison. As above, likelihood ratio tests will be used to assess the significance of fixed effects and interactions in the final model. Again, while a positive effect of biofeedback is hypothesized, we will use a two-sided hypothesis test to be conservative. For this second model, we will additionally test for the presence of a significant time-by-condition interaction in which the magnitude of improvement associated with biofeedback significantly is allowed to vary with time.

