To assess impact on our primary outcome, the acoustic accuracy measure of F3-F2 distance, we will fit a multilevel model using Phase 1 (Acquisition) data. The primary effect of interest is a comparison between MBT and biofeedback treatments, with visual-acoustic and ultrasound biofeedback types pooled for this analysis. This initial model will also adjust for site, performance response category (high responder versus low responder based on a Dynamic Assessment), Acquisition day (1, 2, or 3), and pre-treatment accuracy (mean F3-F2 distance across /i/ sounds in the word probe elicited in the first pre-treatment evaluation). If a within-session time trend is supported by the data, we will extend the model to account for time trends across trials within each day of treatment. Random intercepts will be included to reflect the fact that observations are nested within speakers and words, and random slopes that improve overall model fit (for speaker, acquisition day; for word, performance response category and pre-treatment accuracy) will be retained following model comparison using likelihood ratio tests.

Likelihood ratio tests will also be used to test the hypothesis of an advantage for biofeedback over MBT. Tests will be performed in two different model specifications. In one, the overall effect across days will be tested by focusing on the coefficient on the treatment variable. The other specification will interact the treatment variable with time in order to test whether the effect varies across days, since the hypothesized advantage for biofeedback over MBT could emerge as early as the first day or as late as the third day of Phase 1 (Acquisition). Although a positive effect of biofeedback is hypothesized, two-sided hypothesis tests will be used to be conservative.

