Our second analysis will fit a linear mixed-effects model using word probe data collected in one immediate pre-treatment and one immediate post-treatment session. The outcome variable will reflect the proportion of naïve listeners who rated the /i/ sound in a given production as correct. The model will include an indicator for time point (pre- versus post-treatment) and for treatment group (biofeedback versus MBT), as well as the interaction between them. As was the case for our primary measure, the model will adjust for site, performance response category based on Dynamic Assessment, and pre-treatment accuracy. Random intercepts for speaker, item (the 50 target words making up the probe measure), and listener will be included. Random slopes of response category and pre-treatment accuracy on word will be examined and included only as warranted by model comparison. As above, likelihood ratio tests will be used to assess the significance of the overall treatment effect. Again, while a positive effect of biofeedback is hypothesized, we will use a two-sided hypothesis test to be conservative.

For this second model, we will additionally test for the presence of a significant time-by-condition interaction in which the magnitude of improvement associated with biofeedback significantly is allowed to vary with time. If we observe a difference in our primary measure (Acquisition) but not our secondary measure (Generalization), this will be interpreted as evidence that biofeedback is more efficient, but not more effective, than MBT.

The final analysis will evaluate changes in impact scores from the 11-item survey assessing the social, emotional, and academic consequences of RSE from pre- to post-treatment time points. A mixed model similar to that used in the previous analyses will be fit including time (pre- versus post-treatment), treatment group (biofeedback versus MBT), and the time-treatment interaction as the primary predictors. The model will also adjust for site, performance response category based on Dynamic Assessment, and pre-treatment accuracy. We will again estimate the interaction between time and treatment group to evaluate whether the functional impact of treatment differs across biofeedback versus MBT conditions.

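### The secondary (Generalization) analysis names two tests of treatment and does not say which one decides; with a pre-treatment row in the model, it should be the time-by-group contrast

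*Combined protocol and SAP*

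**What the plan says.** The secondary analysis is described twice, in section 12 (Analysis Plan) and in the Data analysis plan. Both use "word probe data collected in one immediate pre-treatment and one immediate post-treatment session". Both model listener-rated correctness with time point, treatment group and their interaction, and adjust for site, response category and pre-treatment accuracy.

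The tests are worded differently:
- Data analysis plan, second analysis: "As above, likelihood ratio tests will be used to assess the significance of the overall treatment effect". No coefficient, time coding or null model is given.
- Section 12, secondary outcome: "likelihood ratio tests will be used to assess the significance of fixed effects and interactions in the final model". No deciding term is given.
- Both then add: "we will additionally test for the presence of a significant time-by-condition interaction".

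The only overall-effect test described before the secondary analysis belongs to the primary outcome: "In one, the overall effect across days will be tested by focusing on the coefficient on the treatment variable".

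The Data analysis plan attaches a conclusion to the secondary result. If Acquisition shows a difference and Generalization does not, "this will be interpreted as evidence that biofeedback is more efficient, but not more effective, than MBT". It does not say which test establishes the absence of a difference.

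The survey analysis does state what its interaction is for: "We will again estimate the interaction between time and treatment group to evaluate whether the functional impact of treatment differs".

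In the secondary model the speaker has a random intercept only. The candidate random slopes are all by word.

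**The concern.** In the primary analysis all three days fall under treatment, so the treatment coefficient averages treatment effects. The secondary model differs because half of its rows precede treatment. The change that treatment produces is then carried by the interaction, which the plan lists second and as an addition. If the overall test is carried over from the primary analysis, its meaning depends on how time is coded.

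Two things are at stake. If a coefficient that does not estimate the full effect decides, a real Generalization benefit could be missed and reported as a lack of effectiveness. If whichever test is significant may be used, the secondary outcome's type I error generally exceeds 5%, and the efficiency-versus-effectiveness conclusion depends on a choice made after the data are seen.

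**Working it through.** The documents give no power, effect size, SD or alpha for this analysis, so there is no plan figure to reproduce.

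**1. What each term estimates (no assumed inputs).** Write the cell mean as m + a·t + b0·g + d·g·t, with g = 1 for biofeedback, t = 1 for post-treatment, b0 the baseline group difference and d the extra gain with biofeedback. Under randomization b0 has expectation 0.

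| Term | Estimates | b0 = 0, d = 0.10 | b0 = 0.04, d = 0 |
|---|---|---|---|
| Group, pre-treatment as reference | b0 | 0.00 | 0.04 |
| Group, time centred or interaction omitted | b0 + d/2 | 0.05 | 0.04 |
| Group, post-treatment as reference | b0 + d | 0.10 | 0.04 |
| Time-by-group | d | 0.10 | 0.00 |

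Only the interaction gives d whatever the chance baseline difference.

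**2. Illustrative power.** From the documents: 110 children allocated 3:3:4, so 110 × 0.6 = 66 biofeedback and 110 × 0.4 = 44 MBT. Assumed: d = 0.55 post-treatment SD, two-sided 0.05, one value per child per time point, pre-post correlation rho = 0.5, baseline SD s relative to a post-treatment SD of 1, and covariate correlation c with the baseline outcome (c·rho with the post outcome).

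SE factor: sqrt(1/66 + 1/44) = 0.1946.

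- Averaged coefficient: effect 0.275, variance (s² + 1 + 2·rho·s)/4 − (c(s + rho)/2)². At s = 1, c = 0 the variance is 0.75, so z = 0.275/(0.866 × 0.1946) = 1.63 and power is 37%.
- Interaction: effect 0.55, variance s² + 1 − 2·rho·s. At s = 1 the variance is 1, so z = 0.55/0.1946 = 2.83 and power is 81%.
- Post-reference coefficient, no covariate: effect 0.55, variance 1, power 81%.

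| Test | s = 1.0 | s = 0.5 | s = 0.3 |
|---|---|---|---|
| Averaged, c = 0 | 37% | 57% | 67% |
| Averaged, c = 0.8 | 62% | 77% | 81% |
| Averaged, c = 1 | 90% | 90% | 90% |
| Interaction | 81% | 90% | 89% |

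The loss is large with no covariate or a weak one, and vanishes or reverses at c = 1. The plan does not settle c. It defines pre-treatment accuracy only acoustically, as "mean F3-F2 distance across /r/ sounds in the word probe elicited in the first pre-treatment evaluation", whereas the pre-treatment outcome row is listener-rated.

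**3. Type I error if either test may count.** This uses a bivariate normal with the implied correlation of the two estimates. For example, at s = 1, c = 0 the averaged coefficient and the interaction are uncorrelated, so the error is 1 − 0.95² = 9.75%. Over rho 0.3 to 0.7 and s 0.3 to 1.0, averaged coefficient or interaction gives 7.0% to 9.8% at c = 0, about 7% to 9% at c = 0.8, and 5.0% to 7.8% at c = 1.

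**4. Standard error of the interaction.** The probe has 50 words per child per time point. Let true change vary between children with SD v, and let the word-level residual SD be r (both assumed). A child's observed change has variance v² + 2r²/50. The intercept-only model uses about 2(r² + v²/4)/50. With r = 0.3 and v = 0.05 these are 0.0061 and 0.0036, so the true standard error is 1.30 times the modelled one, and type I error is about 13%. Over r = 0.3 to 0.4, simulation gave about 5% at v = 0, 10% to 13% at v = 0.05, and 21% to 31% at v = 0.10. Testing on child-level change gave 5% to 6%. The interaction power in step 2 is for child-level data, not for the intercept-only model.

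**The case against.** The case on the other side has real substance.

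- **The valid contrast is already planned.** This stands. A reader might infer that the plan tests the wrong term. The documents do not support that: the interaction is in the model and will be tested. What is missing is its status.
- **The treatment coefficient need not be the baseline difference or half the effect.** This stands. With post-treatment as the reference level it is the full post-treatment difference, and the plan gives no reference level. The half-effect case needs centred time, or an omitted interaction that would contradict the stated model.
- **A likelihood ratio test makes the baseline-difference reading strained.** Largely right. If time and group enter as factors, dropping the group main effect while keeping the interaction leaves the fit unchanged and gives no degrees of freedom. The natural likelihood ratio test of an overall effect drops both treatment terms. That joint test is valid, but the plan does not describe it, and the opening reference back may concern only the likelihood ratio method.
- **The survey paragraph says the interaction will be estimated again, which suggests the same role in the secondary analysis.** It is a hint. It does not rank the interaction above the overall test or attach the interpretation rule to it.
- **The random slope is a separate matter.** It does not bear on which test decides. It belongs in the fix because the recommended test depends on a valid standard error for the interaction.

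**Conclusion.** The concern holds as a gap in the test hierarchy. The plan names an overall-effect test and an interaction test for the secondary outcome, describes them differently in two places, and leaves open which decides the efficiency-versus-effectiveness conclusion. That much rests on the text alone, as does the dependence of the treatment coefficient on time coding.

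The size is uncertain. The power loss and the type I error of about 7% to 10% for the averaged coefficient or the interaction rest on assumed effect size, SDs and correlations. With a covariate that reproduces the baseline outcome, the power loss disappears and the inflation shrinks to between none and 7.8%. A claim that the secondary analysis will necessarily lose power, or report half the effect, would go beyond the documents.

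The understated standard error under a speaker intercept alone depends on how much children differ in true change, which the documents do not give. The matter should be fixed before analysis, and it does not invalidate the design.

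**What to change.** In both section 12 and the Data analysis plan, using the same wording:

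1. Name the time-by-group contrast, ideally with baseline group means constrained equal, as the single deciding test of the secondary outcome. A post-treatment contrast adjusted for the child's baseline listener-rated accuracy, with the planned random effects, is an acceptable alternative. State the time coding.
2. Drop the overall-effect likelihood ratio test or label it descriptive.
3. Tie the efficiency-versus-effectiveness rule to the deciding contrast.
4. Add a by-speaker random slope for time and keep the other planned random effects.

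The cost is SAP wording, with no new data or procedures. The slope gives a somewhat larger standard error for the interaction if children differ in true change.

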 - Probes for /r/: Sentence, Word, Stimulability
 - Rake-wake discrimination task
 - Bite block task
 - Category goodness task
 - Phonetic awareness task

4. Treatment targets

- Target variants:
 - syllabic /ɛ/, vocalic front vowel context, vocalic back vowel context, consonantal front vowel context, consonantal back vowel context.
- All participants will practice all variants in all phases of treatment.

5. Phase 0: Dynamic assessment

- Dynamic Assessment will consist of a single 90-minute session of traditional motor-based (non-biofeedback) instruction. The goal is to evaluate participants’ stimulability in detail and classify them into stimulability categories for randomization.

MASTER PROTOCOL FOR C-RESULTS RCT

- Same protocol as Phase I: Acquisition (see below), including both pre-practice and structured practice, but with no biofeedback.
 - Instruction (~25 min): Discuss tongue shapes for /r/. Use “Script_Introducing tongue shapes for r_Dynamic_Assessment_CRESULTS,” plus Tiede et al poster, followed by 2-minute break.
 - Pre-practice (until performance criterion met or session-level timer reaches 44 minutes): Relatively unstructured practice guided by the Prepractice Tally Sheet, with model and KP on every trial, followed by a 2-minute break.
 - Structured syllable practice (44 min).
- Based on the treating clinicians’ perceptual ratings of participants’ performance in Phase 0, participants will be categorized as high responders (>5% accuracy during Dynamic Assessment) or low responders (0-5% accuracy).

6. Randomization

- Overview:
 - Randomization will be supervised by the study statistician at the central site (NYU).
 - Randomization will be stratified by site and severity.
 - Randomization will be proportioned in a 3:3:4 ratio (ultrasound biofeedback : visual-acoustic biofeedback : traditional motor-based treatment) at each site.
- Approach:
 - The study statistician will generate confidential participant treatment assignments in batches of 10, where each batch of 10 corresponds to a combination of site (Montclair State University versus Syracuse University) and response category (high versus low).
 - Random assignments will be generated to ensure the following distribution per batch: 3 individuals assigned to receive visual-acoustic biofeedback, 3 to receive ultrasound biofeedback, and 4 to receive MBT.

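### A non-significant Generalization result is to be read as evidence that biofeedback is not more effective than MBT, with no margin or interval criterion and no contrast tied to the rule

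*Combined protocol and SAP*

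**What the plan says.** The rule is in the second analysis of the Data analysis plan. Its condition is "If we observe a difference in our primary measure (Acquisition) but not our secondary measure (Generalization", and its consequence is "this will be interpreted as evidence that biofeedback is more efficient, but not more effective, than MBT". Section 12 (Analysis Plan) describes the same analyses without this rule and gives no other in its place.

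The Generalization model has both probes in the outcome, with "an indicator for time point (pre- versus post-treatment) and for treatment group (biofeedback versus MBT), as well as the interaction between them". It has random intercepts for speaker, item and listener. The only random slopes considered are those of response category and pre-treatment accuracy on word.

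Two tests follow in the Data analysis plan. The first is "As above, likelihood ratio tests will be used to assess the significance of the overall treatment effect". Then "we will additionally test for the presence of a significant time-by-condition interaction". Section 12 says more broadly that "likelihood ratio tests will be used to assess the significance of fixed effects and interactions in the final model". All tests are two-sided.

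For Acquisition, "Tests will be performed in two different model specifications": one tests the effect across days, the other whether that effect changes by day.

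Neither analysis section states a margin, a smallest important difference, a confidence-interval criterion or an alpha.

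**The concern.** A superiority test that fails to reject does not show that there is no benefit. It shows only that the data did not rule out zero. The rule goes further and counts the failure as evidence on the negative side. Nothing in the plan asks whether the estimate is precise enough to exclude a benefit worth having.

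The sentence also speaks of observing a difference without tying that to a test. On the secondary this matters, because the two candidate tests answer different questions. A group effect that includes the pre-treatment probe does not measure how much more one group improved.

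At stake is the contrast between efficiency and effectiveness. If the pattern occurs, the pre-specified text has the trial report that biofeedback is not more effective at the immediate post-treatment probe, possibly with an interval that still contains a useful benefit.

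**Working it through.** The plan has no figure of its own to reproduce here. Enrollment of 110 is given without alpha, power, effect size or SD. The main argument is logical, and the arithmetic only illustrates it.

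**1. Evidence the rule requires.** Condition: a difference on Acquisition and none on Generalization. Test on Generalization: two-sided, null of zero. Conclusion: not more effective. To support that conclusion, the interval for the difference in change would have to lie below some worthwhile benefit. No step in the plan examines this.

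**2. Which contrast.** Let the true benefit be d at the post-treatment probe and 0 at the pre-treatment probe, as randomization implies on average.
- Time-by-group interaction: d − 0 = d.
- Group difference averaged over both probes: (0 + d)/2 = d/2.
- Group coefficient in a model with an interaction and pre-treatment as the reference: 0.

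The phrase overall treatment effect could mean either of the last two, or a joint test of group and interaction. Only the interaction is a direct estimate of differential improvement.

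**3. How wide a child-level interval could be.** Inputs: 110 children (Enrollment, Master Protocol); "Randomization will be proportioned in a 3:3:4 ratio" (Section 6), so pooled biofeedback is 110 × 6/10 = 66 and MBT is 110 × 4/10 = 44. Assumed: two-sided alpha 0.05, no loss, probe score in SD units with equal SD before and after, pre-post correlation r.
- SE0 = √(1/66 + 1/44) = 0.195.
- SE of the difference in change = SE0 × √(2(1 − r)).
- r = 0.5: SE = 0.195, half-width 1.96 × 0.1946 = 0.38 SD.
- r = 0.7: SE = 0.1946 × √0.6 = 0.151, half-width 0.30 SD.

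An estimate of 0.2 SD at r = 0.5 would be non-significant, with an interval from about −0.18 to 0.58 SD.

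**4. Why the planned model may not give that interval.** It has no by-speaker slope for time. If children differ in how much they change, a random-intercept model puts that variation into the word-level residual and divides it by the number of words. Further assumptions: r = 0.5, one value per word and time point, 50 words, word-level noise variance s² of 1 to 5 (not in the documents).
- Child-by-time variance v = 0.5 − s²/50: 0.48 at s² = 1, 0.40 at s² = 5.
- Residual variance the model would estimate ≈ s² + 50v/99: 1.24 and 5.20.
- Model SE = SE0 × √(2 × residual/50): 0.043 and 0.089.
- Half-width = 1.96 × SE: 0.09 and 0.17 SD, against 0.38 SD at child level.

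Fitting the random-intercept model (speaker only) to simulated data gave the same SEs, 0.043 and 0.089. So the interval from the model as written could be less than half as wide as it should be.

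**The case against.** The rule is cautious in one direction. It works against the sponsor's hypothesis and stops an Acquisition-only result from being presented as greater effectiveness. It covers one scenario on a secondary outcome, nothing prevents the estimate and interval from being reported beside it, and not more effective can be read as not shown to be more effective. The protection is real and should be kept. The charitable reading is not what the sentence says, and it costs little to write it down.

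A reader might infer that the plan leaves the deciding tests wholly open. That goes too far. The primary specifications have different jobs, with the pooled comparison named as the effect of primary interest. On the secondary, the overall effect comes first and the interaction is additional. A default reading exists. What stands is that the rule is not tied to it, and that for Generalization the default is the less suitable contrast.

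A reader might also use the 0.38 SD half-width to say how often a true benefit would be missed, and conclude that under-claiming for biofeedback is the likely error. The documents do not support this. The planned model's standard error could be much smaller (step 4), in which case Generalization differences might be declared too readily and the rule would fire less often. The same uncertainty argues against adding a margin: the documents supply no smallest worthwhile difference, and an interval that is too narrow would meet a margin too easily.

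**Conclusion.** The concern holds as a defect of interpretation. In one pre-specified scenario, the Data analysis plan converts a non-significant superiority test into a negative conclusion without a margin or interval to support it, and it does not say which contrast triggers the conclusion. This follows from the text and does not depend on any assumed number.

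The size is illustrative only. Under the assumptions in step 3, a child-level interval reaches about 0.38 SD either side of the estimate (0.30 SD at correlation 0.7), which is wide enough for a null result to sit beside a moderate benefit. These are not figures for the planned model, whose precision depends on variance components that the documents do not give.

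The text gives no ground for inferring that the primary analysis, the estimates or the type I error of the primary comparison are harmed by this rule. It should be fixed before the results are interpreted, but it is limited in reach.

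**What to change.** Replace the interpretation sentence with:

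*If the primary overall treatment effect shows a difference and the time-by-group interaction for Generalization does not, we will report the biofeedback-versus-MBT difference in pre-to-post change in p-hat-correct with its 95% CI and state that greater effectiveness on Generalization was not demonstrated; we will not conclude that biofeedback is not more effective.*

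Make the interval reflect between-child variation in change, for example with a by-speaker random slope for time or a child-level analysis of change. Put the same wording in Section 12, so that the two analysis sections agree.

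This needs no new data and no change in sample size. The costs are a weaker statement when the secondary is null and one extra variance term, which will probably widen the Generalization interval. The protection against over-claiming from Acquisition alone is kept.
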